6.9 Management of Adverse Events of Special Interest

Adverse events of special interest (AESI) are serious or nonserious AEs specific to the known mechanism of action of the study intervention that are of clinical interest.

For this study, AESIs include the following:

- Infusion-related reactions including immediate hypersensitivity
- Immune-related AEs
- TGF- β inhibition mediated skin reactions
- Anemia
- Bleeding AEs

6.9.1 Infusion-related Reactions Including Immediate Hypersensitivity

Infusion-related reactions including immediate hypersensitivity, are defined in this section. Infusion-related reactions are AESIs and identified risks for bintrafusp alfa.

Infusion-related Reactions

Infusion-related reactions are defined as any signs or symptoms experienced by participants during the infusion of pharmacologic or biologic agents or any event occurring during or within 1 day of study intervention administration. They are identified based on a list of Medical Dictionary for Regulatory Activities (MedDRA) preferred terms and criteria on the timely relationship to an infusion. Events are divided into reactions versus signs and symptoms:

- Reactions are considered when onset is on the day of infusion (during or after the infusion) or the day after the infusion (irrespective of resolution date) for IRR, drug hypersensitivity, anaphylactic reaction, hypersensitivity, and type 1 hypersensitivity.
- Signs and symptoms of IRR and hypersensitivity/allergic reactions are considered when onset is on the day of infusion (during or after the infusion) and resolved completely with the end date within 2 days after onset of (but not limited to) pyrexia, chills, flushing, hypotension, dyspnea, wheezing, back pain, abdominal pain, and urticaria.

Management of Infusion-related Reactions

Premedication prior to bintrafusp alfa administration for the first 2 infusions is optional and at the discretion of the Investigator. If an Investigator chooses to administer premedications, premedication with an antihistamine and with paracetamol (acetaminophen) (e.g., 25 to 50 mg diphenhydramine and 500 to 650 mg paracetamol [acetaminophen] IV or oral equivalent) approximately 30 to 60 minutes prior to each dose of bintrafusp alfa is recommended.

If Grade ≥ 2 infusion reaction(s) are seen during the first 2 infusions, premedication should be continued/implemented for future infusions.

An assessment for possible IRR should be triggered based upon the development of specific symptoms within 24 hours of an infusion.

Management of symptoms should follow the guidelines shown in **Error! Reference source not found.**

Table 5 Treatment Modification of Bintrafusp alfa for Symptoms of Infusion-related Reactions Including Immediate Hypersensitivity

NCI-CTCAE v5.0 Grade	Treatment Modification

Grade 1 – mild
 
 Mild transient reaction; infusion interruption not indicated; intervention not indicated. 	
 Increase monitoring of vital signs as medically indicated as participants are deemed medically stable by the attending Investigator.

Grade 2 – moderate
 
 Therapy or infusion interruption indicated but if responds promptly to symptomatic treatment (e.g., antihistamines, NSAIDs, narcotics, IV fluids); prophylactic medications indicated for ≤ 24 hours. 	
 Stop the infusion of the study intervention-caused IRR. Increase monitoring of vital signs as medically indicated as participants are deemed medically stable by the attending Investigator. If symptoms resolve quickly or decreased to Grade 1, resume infusion at 50% of original rate with close monitoring of any worsening otherwise dosing held until resolution of symptoms with mandated premedication for the next scheduled visit. If worsens to Grade 3 or 4, follow treatment modification guidelines accordingly.

Grade 3 or Grade 4 – severe or life-threatening
 
 Grade 3: Prolonged (e.g., not rapidly responsive to symptomatic medication and/or brief interruption of infusion); recurrence of symptoms following initial improvement; hospitalization indicated for clinical sequelae. Grade 4: Life-threatening consequences; urgent intervention indicated. 	
 Stop the infusion of study intervention-caused IRR immediately and disconnect infusion tubing from the participant with additional appropriate medical measures and closely monitor until deemed medically stable by the attending Investigator. Hospitalization and/or close monitoring is recommended. Administration of glucocorticoids may be required Restart the medication taking out the drug that is the cause of IRRs from the next scheduled visit

IRR=infusion-related reactions, IV=intravenous, NCI-CTCAE=National Cancer Institute-Common Terminology Criteria for Adverse Event, NSAIDs=nonsteroidal anti-inflammatory drugs. Once the bintrafusp alfa infusion is interrupted or rate reduced to 50% of previous infusion rate, it must remain decreased for all subsequent infusions. For Grade 3 or 4 IRRs, bintrafusp alfa discontinuation is mandated. For all types and grades of infusion reactions, details about drug physical constitution, method of preparation, and infusion must be recorded.
	

In the event of a Grade 2 IRR that does not improve or worsens after implementation of the treatment modifications indicated in [Table 5](#) (including reducing the infusion rate by 50%), the Investigator may consider treatment with corticosteroids and the infusion should be stopped for that day. At the next infusion, the Investigator may consider the addition of H2 blocker antihistamines (e.g., famotidine or ranitidine), in addition to the above provided recommended optional premedication regimen, for selected participants. However, prophylactic steroids are not permitted. At the next dose, if the participant has a second IRR Grade ≥ 2 on the slower infusion

rate, with the addition of further medication to premedication, the infusion should be stopped, and the Investigator may consider withdrawal of this participant from the study.

Hypersensitivity Reaction

If a hypersensitivity reaction occurs, the participant must be treated according to the best available medical practice. A complete guideline for the emergency treatment of anaphylactic reactions according to the Working Group of the Resuscitation Council United Kingdom and can be found at <https://www.resus.org.uk/pages/reaction.pdf>. Participants should be instructed to report any delayed reactions to the Investigator immediately.

Symptoms may include, but are not limited to:

- Impaired airway
- Decreased oxygen saturation (< 92%)
- Confusion
- Lethargy
- Hypotension
- Pale/clammy skin
- Cyanosis.

Management of hypersensitivity includes:

- Epinephrine injection and IV dexamethasone
- Participant should be placed on cardiac, blood pressure, heart rate, and oxygen saturation monitoring immediately
- Alert intensive care unit for possible transfer if required.

Prophylaxis of Flu-like Symptoms:

For prophylaxis of flu-like symptoms, a nonsteroidal anti-inflammatory drug (NSAID), e.g., ibuprofen 400 mg or comparable NSAID dose, may be administered 2 hours before and 8 hours after the start of each IV infusion.

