7.1 Discontinuation of Study Intervention

Participants may be discontinued from study intervention for any of the following reasons, one reinitiating course of treatment may be allowed (see Section 7.1.2.1).

- A participant may discontinue from the study intervention at any time at his/her own request (i.e., withdrawal of consent), and without giving a reason.
- Occurrence of an exclusion criterion, which is clinically relevant and affects the participant's safety, if discontinuation is considered necessary by the Investigator and/or Sponsor.
- A participant may be discontinued at any time at the discretion of the Investigator for safety, behavioral, compliance, or administrative reasons (See Section 6.8 and 6.9 for TEAEs and AESIs that require treatment discontinuation).
- Confirmed PD per RECIST 1.1, with the exception that participants receiving treatment may continue past PD if the participant's ECOG PS has remained at least stable, and if in the opinion of the Investigator, the participant will benefit from continued treatment (See Section 7.1.3).
- Unacceptable toxicity.
- Some TEAEs and AESIs require withdrawal from treatment. See Section 6.8 and 6.9 for additional details.
- Drug must not be given to a known pregnant participant (refer to Appendix 3).
- Use of a prohibited concomitant drug, as defined in Section 6.5.2, where the predefined consequence is withdrawal from the study intervention.

The SoA specifies the data to collect at study intervention discontinuation and follow-up and any additional evaluations that need to be completed.

In case of discontinuation from the study intervention:

- The day of End-of-Treatment will correspond to the day of withdrawal (or within 7 days).
- An attempt should be made to perform all assessments scheduled for the End-of-Treatment visit if possible. If not possible, the most clinically relevant assessments and appropriate eCRFs for the End-of-Treatment visit should be prioritized as feasible.
- Participants will be asked to continue Safety and Survival Follow-up, which includes the collection of data on survival, patient-reported outcome (PRO) questionnaires, and subsequent

anticancer therapy. After completion of the follow-up period or after the End-of-Treatment visit, whichever is applicable, the appropriate eCRF section for Study Termination must be completed.

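### Protocol 6.9.1 gives inconsistent instructions for infusion reactions that do not settle promptly and for a second reaction that is the first to reach Grade 3

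*Protocol*

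**What the plan says.** All of the following is in Protocol 6.9.1 unless another section is named.

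- **Table 5, Grade 2 row.** Grade 2 needs treatment or an interruption but responds promptly. If symptoms settle quickly or fall to Grade 1, the infusion resumes at half rate. If not, dosing is held until symptoms resolve, and premedication is required at the next visit. A reaction that worsens to Grade 3 or 4 is sent to the Grade 3/4 guidance.
- **Table 5, Grade 3 definition.** A prolonged reaction, "not rapidly responsive to symptomatic medication and/or brief interruption of infusion); recurrence of symptoms following initial improvement".
- **Table 5, Grade 3/4 action.** Stop at once, and also: "Restart the medication taking out the drug that is the cause of IRRs from the next scheduled visit".
- **Table 5 footnote.** "For Grade 3 or 4 IRRs, bintrafusp alfa discontinuation is mandated".
- **Paragraph after the table.** "In the event of a Grade 2 IRR that does not improve or worsens after implementation of the treatment modifications indicated in" Table 5 (the half rate included), "the Investigator may consider treatment with corticosteroids and the infusion should be stopped for that day". It continues: "At the next infusion, the Investigator may consider the addition of H2 blocker antihistamines".
- **Second reaction.** For a second IRR of Grade 2 or above at the slower rate with added premedication, "the infusion should be stopped, and the Investigator may consider withdrawal of this participant from the study".
- **Section 6.8.** It refers IRR guidance to 6.9.1. Its general rules require permanent discontinuation for related Grade 4 events and for related Grade 3 reactions that recur, each with listed exceptions.
- **Sections 7.1 and 7.2.** After stopping treatment, "Participants will be asked to continue Safety and Survival Follow-up". Leaving the study is a separate step, which the Investigator may also initiate for safety.

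**The concern.** Two investigators with the same patient could act differently and both cite 6.9.1. One would treat a reaction that has not improved as Grade 3 and discontinue bintrafusp alfa. The other would keep it as Grade 2, stop for the day and dose at the next visit. A similar split arises when a second reaction reaches Grade 3, because one sentence is mandatory and the next is discretionary.

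The main stake is participant safety, since the instruction matters most when a reaction is not settling. The statistical stake is smaller. SAP 15.2.3.1 tabulates IRRs leading to permanent treatment discontinuation, and the reduced analysis list in SAP 6.1 keeps adverse events of special interest and events leading to discontinuation. Those counts would partly reflect which sentence a site followed.

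**Working it through.** The plan gives no figure to reproduce on this point. The check sets the rules side by side, case by case.

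| Case | Text that stops the drug | Text that foresees another infusion or leaves discretion |
|---|---|---|
| 1. First reaction, not improving after interruption and treatment | Fits the Grade 3 definition, so the footnote applies | Grade 2 row's hold-and-resume branch; paragraph after the table |
| 2. First reaction improves, infusion resumes at half rate, symptoms return | Fits the Grade 3 definition (recurrence), so the footnote applies | Paragraph after the table |
| 3. First reaction worsens and is graded 3 or 4 | Grade 2 row's escalation clause, then the footnote | None, once the escalation clause is read in |
| 4. Second reaction, Grade 2 | None mandatory | Discretionary sentence; no conflict with the footnote |
| 5. Second reaction, the first to reach Grade 3 | Footnote only; the 6.8 rule on recurrent Grade 3 does not reach it | Discretionary sentence |
| 6. Second reaction, Grade 4 | Footnote, and 6.8 subject to its exceptions | Discretionary sentence |

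**Case 1.** Table 5 makes a prompt response part of Grade 2, and lack of a rapid response the mark of Grade 3. A reaction that does not improve fails the first and meets the second. The Grade 2 row nevertheless contains a branch for reactions that do not settle quickly, and that branch leads to dosing at the next visit. So part of the conflict lies inside Table 5. Neither prompt nor rapid is given a time limit, so the grade itself turns on judgement.

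**Case 2.** Table 5 permits the half rate only after symptoms have settled or fallen to Grade 1. The paragraph's trigger includes a reaction after that rate cut. Symptoms that return at the half rate are a recurrence after improvement, which is Grade 3 wording.

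**Case 5.** The lower bound of Grade 2 has no matching upper bound, so Grade 3 is included. The footnote is mandatory; the sentence says the Investigator may consider withdrawal. Section 6.8 does not settle it: its Grade 3 stopping rule is for reactions that recur or persist for 12 weeks, and it sends IRR guidance back to 6.9.1 without an order of precedence.

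**Size.** Inputs: about 135 participants (Protocol 4.1) and related IRRs below 5% (Protocol 2.3).

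0.05 × 135 = 6.75

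That is fewer than 7 participants with any related IRR. Section 2.3 adds that the observed reactions were Grade 1 or 2 and did not require permanent discontinuation. The number reaching cases 1, 2, 5 or 6 should therefore be well below 7, and may be zero.

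**The case against.** The best defence is that the surrounding text already answers much of this.

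- **Escalation clause.** A reader might infer that the paragraph re-doses patients whose reaction has worsened to Grade 4. The documents do not support that. The paragraph is limited to Grade 2, and the Grade 2 row sends worsening to Grade 3 or 4 elsewhere. This stands for that limb, but it does not reach a reaction that fails to improve.
- **Agreement between text and table.** The Grade 2 row also foresees holding and then dosing at the next visit, so it is too simple to say that the text re-doses where the table stops. This stands, and it moves part of the conflict into the table rather than removing it.
- **Section 6.8.** It separately covers Grade 4 and recurrent Grade 3 events. This stands, with its exceptions, and leaves case 5 as the clearest gap.
- **Discontinuation need not be final.** The footnote does not say permanent, and 7.1.2.1 allows one reinitiation after an adverse event that is managed or resolved, with the Medical Responsible's agreement. So the two readings are not always strict opposites. But reinitiation has its own conditions and is not the routine next dose that the paragraph describes.
- **Leaving the study differs from stopping the drug.** Both sentences could hold literally for a second Grade 3 reaction. However, the second-reaction sentence is the only one directed at that event, so a site may well take it as the decision about the drug.
- **Grading is external.** Severity follows NCI-CTCAE v5.0, so the action sentences do not by themselves change the grade distribution. This largely stands.

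**Conclusion.** The inconsistency is real and visible in adjacent text. It has two parts: reactions that do not settle promptly, where the Grade 2 branch and the following paragraph conflict with the Grade 3 definition and footnote; and second reactions, most clearly one that is the first to reach Grade 3.

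Two further wording points are secondary. The bullet on restarting medication without the causal drug does not fit a monotherapy trial. A reader might take it as an order to re-expose, but with a single agent it leaves nothing to restart. The reference to withdrawal from the study should be checked against the distinction between 7.1 and 7.2. A reader might call it a contradiction of 7.1, but 7.2 permits such withdrawal, and the participant stays in the full analysis set, which is everyone dosed. Literal use could still cost follow-up.

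The size is small and confined to the IRR safety tables, mainly the count leading to permanent discontinuation. The primary analysis of response does not rest on these rules. The estimate assumes that the rate seen at study initiation carries over to this trial. It refers to related IRRs, whereas SAP 15.2.3.1 identifies IRRs by preferred term and timing whatever the attribution, so the tabulated number could be higher. The point merits correction because it concerns a safety instruction, not because of its numerical weight.

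**What to change.** The sponsor should reconcile six places so that each graded event leads to one action: the Table 5 grade definitions, the Grade 2 actions (including the hold-and-resume branch), the Grade 3/4 actions, the footnote, the paragraph after the table, and Section 6.8. Changing the paragraph alone would leave the conflict inside Table 5. The reconciled text should state:

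- what applies to a reaction that does not improve, or returns after improvement;
- what applies to a second reaction at each grade, including one that is the first to reach Grade 3;
- which section prevails where 6.8 and 6.9.1 both apply;
- whether the restart bullet has a meaning in this trial;
- whether stopping treatment or leaving the study is meant after a second reaction.

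Which rule stands is the sponsor's medical decision, and no view is taken here. Sites should be told of the outcome. The cost is wording in 6.9.1 and 6.8 and a communication to sites; no extra participants, procedures or SAP analyses are needed.

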6.9.2 Immune-related Adverse Events

Immune-related AEs are specific to immunotherapies and vary by organ system. Immune-related AEs are considered AESIs.

In general, the spectrum of irAEs is similar for bintrafusp alfa compared with other checkpoint inhibitors. Effective risk management of these toxicities (irAEs) primarily caused due to inhibition of PD-L1 and PD-1 pathways, is based on key recommendations ([Champiat 2016](#)). Participant education for on-time reporting of symptoms of potential irAEs and prompt clinical assessment is critical for effective management and quicker resolution of immune-mediated toxicities, thus

preventing progression into severe forms of toxicity that otherwise may become life-threatening and difficult to manage or warrant permanent discontinuation from the study.

The following irAEs are important identified risks for bintrafusp alfa:

- Immune-related hepatitis
- Immune-related pneumonitis
- Immune-related colitis
- Immune-related nephritis and renal dysfunction
- Immune-related endocrinopathies (thyroid disorders, adrenal insufficiency, type 1 diabetes mellitus, pituitary disorders)
- Immune-related rash
- Other immune-related events (myositis, myocarditis, encephalitis)

The following irAEs are important potential risks for bintrafusp alfa:

- Guillain-Barré syndrome
- Uveitis
- Pancreatitis
- Myasthenia gravis/myasthenic syndrome

The Medical Monitor may be involved as needed for follow-up. Details of the diagnostic work-up will be requested by the study team.

Recommended guidance and management for specific irAEs as per published guidelines as provided in [Appendix 5](#). These recommendations are in accordance with the joint American Society of Clinical Oncology (ASCO) Clinical Practice Guidelines ([Brahmer 2018](#)) and National Comprehensive Cancer Network ([NCCN 2018](#)) guidelines.

Treatment of irAEs is mainly dependent upon severity as defined by NCI-CTCAE v5.0. In general, management by NCI-CTCAE v5.0 grading is listed below:

- Grade 1: study intervention should be continued with close monitoring, with the exception of some neurologic, hematologic, and cardiac toxicities.
- Grade 2: study intervention may be suspended for most Grade 2 toxicities, with consideration of resuming when symptoms revert to Grade 1 or less. Corticosteroids may be administered (initial dose of 0.5 to 1 mg/kg/day of prednisone or equivalent).
- Grade 3: study intervention is generally suspended and the high-dose corticosteroids (prednisone 1 to 2 mg/kg/day or methylprednisolone 1 to 2 mg/kg/day) treatment should be initiated. Corticosteroids should be tapered over the course of at least 4 to 6 weeks. Some refractory cases may require infliximab or other immunosuppressive therapy.

- Grade 4: in general, permanent discontinuation of study intervention is recommended, with the exception of endocrinopathies that have been controlled by hormone replacement.

Permanent treatment discontinuation is required in case of immune-related Grade 4 rash/inflammatory dermatitis, nephritis, autoimmune hemolytic anemia, hemolytic uremic syndrome, aplastic anemia, immune thrombocytopenia, acquired thrombotic thrombocytopenic purpura, inflammatory arthritis, myositis, and polymyalgia-like syndrome.

For Grade 4 immune-related lymphopenia, permanent treatment discontinuation will be required, if lymphopenia is considered immune-related in nature, no clear alternative explanation exists for the event, and Grade 4 lymphopenia does not resolve within 14 days. Permanent treatment discontinuation is not required when the AE is manifest by a single laboratory value out of normal range without any clinical correlates. In this case, treatment should be held until the etiology is determined. If the event is not considered immune related and resolves to Grade ≤ 1 restarting treatment may be considered.

- For Grade 1 immune-related pneumonitis: continue treatment. If clinically indicated, monitor participants weekly or more frequently as needed with history, physical examination, and pulse oximetry. If symptoms appear and/or changes in the physical examination are noted, treat as Grade 2.
- For myositis: in case of management with rituximab, treatment should be discontinued.

For organ/system specific management guidelines, see the guideline tables in [Appendix 5](#).

Recommended guidance and management for specific irAEs are provided in the current NCCN guideline available at <http://www.nccn.org>.

6.9.3 TGF- β Inhibition Mediated Skin Reactions

TGF- β inhibition mediated skin reactions, including hyperkeratosis, KA, and/or cSCCs, are important identified risks and AESI for bintrafusp alfa.

Skin assessments are performed at Screening period and every 6 weeks for all participants per SoA (see [Table 1](#)). Baseline skin assessments include a detailed medical history of genetic or iatrogenic skin conditions, skin type, significant UV exposure/sun damage of skin, geographical location, and occupational or environmental exposure to radiation or chemicals.

Skin AEs appear to be related to both mechanisms of bintrafusp alfa; anti-PD-L1 and anti-TGF- β :

1. Immune-related skin AEs possibly mediated by PD-L1 inhibition (e.g. rash or maculo-papular rash, distributed typically on trunk and uniformly on limbs). Just as immune-related AEs to other organs (see [Section 6.9.2](#)), immune related AEs affecting the skin are important identified risks for bintrafusp alfa and AESI.

Immune-related skin AEs should be managed according to the recommended guidance and management for specific irAEs as per published guidelines (refer to [Appendix 5](#)). Treatment

typically include use of emollients, non-sedating antihistamines for pruritus, targeted use of potent topical steroids to most inflamed lesions; oral corticosteroids in highly symptomatic case.

2. Skin AEs, possibly due to TGF- β inhibition, including hyperkeratosis, KA and/or cSCC, are important identified risks and AESI for bintrafusp alfa. The distribution of lesions tends to be in sun-exposed areas. These AEs are AESIs for bintrafusp alfa.

Management guidelines for potential TGF- β inhibition mediated skin reactions are:

1. Discontinuation or interruption is not required in most cases. Continuation of treatment should be evaluated by the Investigator.
2. Emollients may continue to be used.
3. Diagnostic and treatment plan should be developed in collaboration between Investigator and dermatologist. In general, treatment of TGF- β inhibition mediated skin lesions such as hyperkeratosis, KA and cSCC should be based on local guidelines/standard of care. Lesion evaluation should include excision biopsy of one representative lesion to confirm diagnosis.
4. Treatment and follow-up for KA and cSCC will depend on number and localization of lesions.
 - For single lesions: Full excision may be recommended.
 - In case of multiple lesions or location not suitable for full excision, other treatment options may be offered by the dermatologist, such as:
 - Mohs surgery, cryotherapy, or other standard treatment options depending on the pathology
 - Use of retinoids, if recommended by dermatologist, may be considered after discussion with Medical Monitor
5. Close clinical follow-up for re-evaluation, resolution, or potential recurrence should be implemented.
6. Spontaneous resolution of KA lesions without surgical intervention has been observed, typically occurring within weeks after discontinuing bintrafusp alfa.
7. The number and localization of lesions, diagnosis (including histopathological diagnosis), treatment, and outcome should be appropriately documented in the eCRF.

Consult with study Medical Monitor, as needed, for management of TGF- β inhibition mediated skin reactions.

